## 1 Protocol Summary

Name of study	Clinical Trial for Pre-market Registration of Biotronik Qubic Stim Cardiac Stimulator
Purpose of study	To prove the clinical effectiveness and safety of Qubic Stim Cardiac Stimulator in Chinese population.
Study design	The trial is a multicenter, prospective and single-arm study. 106 appropriate subjects were selected from 3 study sites in China in accordance with the inclusion and exclusion criteria. The subjects consent to participate in the trial and sign the informed consent. The subjects who meet the inclusion and exclusion criteria will receive the intracardiac electrophysiological examination, during which the subjects will be subject to diagnostic electrical stimulation by the Qubic Stim Cardiac Stimulator. The subjects will also receive the clinical follow-up visit after cardiac electrical stimulation until they are discharged from the hospital. The clinical effectiveness and safety of Qubic Stim Cardiac Stimulator in Chinese population were proved by observing the data collected in this study.
Sample size	106 cases
Study site	3 study sites in China
Investigational device	Qubic Stim Cardiac Stimulator
Study population	Patients with indications for intracardiac electrophysiological examination
Study period	Enrollment time of the first batch of subjects: October 2020 Expected inclusion period: 3 months End of follow-up: Feburary 2021
Inclusion criteria	

1. Age <math>\geq</math> 18 years

2. Subjects who are willing to participate and sign the informed consent form, and are able to finish the follow-up at the study site.

3. Subjects with an indication of the intracardiac electrophysiological examination(fit one of the following):

➤ Paroxysmal supraventricular tachycardia: atrioventricular reentrant tachycardia or atrioventricular node reentrant tachycardia or atrioventricular tachycardia

➤ Ventricular arrhythmia: Premature ventricular contraction or ventricular tachycardia.

➤ Atrial fibrillation

➤ Atrial flutter

Exclusion criteria	

1. Previous cases of unsuccessful radiofrequency ablation or recurrence

2. Pregnant and/or lactating women

3. Acute or severe systemic infection was present within 7 days prior to the intracardiac electrophysiological examination

4. Liver and kidney functions were obviously abnormal within 7 days prior to the

	
intracardiac electrophysiological examination
 
 
5. Obvious bleeding tendency or blood system disease
 
6. Cancer and terminal disease
 
7. Combined with severe organic cardiovascular disease
 
8. Cerebral apoplexy and other cerebrovascular diseases within the past 3 months
 
9. Thromboembolic disease
 
10. Subjects who are participating in other interventional clinical trials
 

Primary clinical observation indexes	
The success rate of the Qubic Stim cardiac stimulator to send diagnostic electrical stimulation to the heart. The success standard refers to that all the main functions of the cardiac stimulator meet the success standards, including:
 
 
1. Programmed extrastimulation (PES)
 
 
Expected clinical effect: PES can effectively pace the heart at a set rate of stimulation.
 
 
2. High Rate (Burst)
 
 
Expected clinical effect: when the tachycardia is induced or terminated by high rate stimulation, this device can effectively pace the heart according to the set stimulating frequency.
 
 
3. Measurement of Sinus node recovery time (SNRT)
 
 
Expected clinical effect: SNRT can be measured.
 
This trial will conduct cardiac electrical stimulation by the main functions of the cardiac stimulator above. Only when the above three functions all reach the standards in particular subjects, it is judged as stimulation success. The main evaluation index corresponds to the proportion of the patients who achieve the success standards.

Secondary clinical observation index	Serious device adverse events caused by cardiac stimulator
Follow-up arrangement	
 
1. Baseline evaluation: when the subjects were enrolled.
 
2. Electrical cardiac stimulation: the period during which the subjects receive the intracardiac electrophysiological examination.
 
3. Pre-discharge assessment
 

Sponsor	BIOTRONIK SE & Co.KG

## 4 Purpose and Content of Clinical Trial

### 4.1 Purpose

It is intended to prove the clinical effectiveness and safety of Cubic Stim Heart Stimulator in Chinese population.

## 4.2 Content

This is a multicenter, prospective and single-arm study. 106 appropriate subjects were selected from 3 study sites in China in accordance with the inclusion and exclusion criteria. The subjects who meet the inclusion and exclusion criteria will receive the intracardiac electrophysiological examination after signing the informed consent, during which the subjects will be subject to diagnostic electrical stimulation by the Qubic Stim Cardiac Stimulator. The subjects will also receive the clinical follow-up after cardiac electrical stimulation until they are discharged from the hospital. The clinical effectiveness and safety of Qubic Stim Cardiac Stimulator in Chinese population were further demonstrated and proved by observing the data collected in this study.

## 5 Background Information of Clinical Trial

Intracardiac electrophysiological (EP) examination is widely used to evaluate cardiac conduction disturbance and arrhythmias. The risks associated with this procedure, particularly the use of an extracorporeal programmed stimulator, are generally acceptable and the patient benefits are considered to outweigh the risks. Diagnostic EP examination is usually combined with the treatment of a diagnosed heart disease, such as catheter ablation of arrhythmia. In addition, the results of EP examination may indicate the need for specific drugs or implantation of a pacemaker or cardioverter defibrillator for treatment.

As a manufacturer of implantable cardiac stimulator and ablation catheter, BIOTRONIK SE & Co.KG has marketed more than 1,300 extracorporeal programmed stimulators for EP examination since 1982, including UHS 20 device and the updated UHS 3000. Both of the devices are used for clinical EP examination. Qubic Stim device is an iterative product of UHS 3000 Universal Cardiac Stimulator. The two devices have similar operation function, intended use and indications. Other medical device manufacturers active in the cardiac EP diagnosis and treatment market also provide a series of extracorporeal programmed stimulators, which are used in the same clinical environment as Qubic Stim device.

The clinical evaluation of Qubic Stim Stimulator (software release version UHS\_SE1.9; UHS\_BE1.8) and PK-128 patient-end cable is provided by BIOTRONIK SE & Co.KG in accordance with the requirements of MEDDEV 2.7.1 Guidelines for Clinical Evaluation of Medical Devices. No uncertain risk emerged in the risk management process of Qubic Stim device and PK-128 patient-end cable based on published literature in the public domain, manufacturer's clinical

experience and results of device availability test. The safety and performance of the device are well validated by clinical evaluation. This medical device meets the basic requirements of European Union (EU) Medical Device Directive. In Europe no further clinical data is needed to prove the safety of Qubic Stim device and PK-128 patient-end cable. This device is clinically equivalent to the most advanced commercially available competitor device, and Qubic Stim performance is suitable for the most advanced EP diagnostic stimulation.

## **6 Product Characteristics, Structure Composition, Operating Principle, Action Mechanism of Product and Trial Stretch**

### **6.1 Product characteristics**

Qubic Stim system is an active and non-invasive medical device runs on software, which is mainly used in combination with other diagnostic medical devices. The Qubic Stim control units and stimulation units are provided in a non-sterile manner and are not suitable for sterilization.

PK-128 patient-end cable is sterile and can be re-sterilized in sterile area. However, the patient-end cable is connected to other equipment (see Figure 1) in current clinical practice, in which case the patient-end cable does not enter the sterile area and does not need sterilization.

The Qubic Stim device is used for invasive cardiac surgery based on its intended application.

### **6.2 Product structure, operating principle and action mechanism**

#### **6.2.1 System structure and settings**

Qubic Stim system includes control unit and stimulation unit, which are connected with each other via Ethernet cable (VK-118). Although software release version UHS\_SE1.9; UHS\_BE1.8 supports the single control unit, stimulation unit hardware is still used to connect two separate control units for future development. The stimulation unit is connected to other devices through PK-128 patient-end cable. An overview of typical device connection including the Qubic Stim system and PK-128 patient cable is shown in Figure 1. Details about PK-128 patient-end cable are shown in Figure 2.

[figure not shown]

Fig. 1: Typical setting of electrophysiological examination and catheter ablation

[figure not shown]

Fig. 2: PK-128 patient-end cable

### 6.2.2 Operating principle and action mechanism

Qubic Stim system is designed to provide the following stimulation modes:

- Programmed extra stimulation (PES);
- Theta burst stimulation or high rate stimulation (Burst);
- Measurement of sinus node recovery time (SNRT)

All parameters can be set on the control unit to control the device operation. The device is programmed and operated through the touch screen and other controls on the control unit. The whole operation of the system is controlled by software. The programmed stimulus plan can be saved and downloaded at an appropriate time.

### 6.3 Trial stretch

This Qubic Stim device is suitable for all patients who need cardiac electrophysiological examination which conducts diagnostic electrical stimulation on the patients during the examination. Therefore, the patients who have the indications of the intracardiac electrophysiological examination and are able to and willing to complete the intracardiac electrophysiological examination will participate in this trial.

---

 PES also means programmed extrastimulation, which specifically refers to adding extra stimulation to the heart rhythm to cause arrhythmia. Programmed extra stimulation is a more general term, including extra stimulation and other stimulation modes.

## **7 Indications, Contraindications and Precautions of the Product**

### **7.1 Indications**

The device is intended for diagnostic electrical stimulation of the heart, including induction and termination of tachyarrhythmia, refractory period measurements and electrical conduction measurements.

Qubic Stim stimulator has the following main functions:

- Programmed extrastimulation (PES)
- High rate stimulation (Burst)
- Measurement of sinus node recovery time (SNRT)

Qubic Stim is suitable for all patients receiving electrophysiological examination. Therefore, the medical indication of the device is the same as that of electrophysiological examinations which require or do not require catheter ablation for treatment.

### **7.2 Contraindications**

Qubic Stim is not suitable for permanent and non-monitoring applications as an external pacemaker.

## **8 Overall Design**

### **8.1 Trial design**

#### **8.1.1 Trial objective**

It is intended to prove the clinical effectiveness and safety of Qubic Stim cardiac stimulator in Chinese population.

### **8.1.2 Selection of test method and reasons**

A multicenter, prospective and single group method is adopted in this study. 106 subjects are selected from 3 study sites in China. The clinical evaluation of Qubic Stim stimulator and PK-128 patient-end cable provided by BIOTRONIK SE & Co.KG in accordance with MEDDEV 2.7.1 “*Guidelines for Clinical Evaluation of Medical Devices*” has well verified the safety and performance of the device. In addition, due to the mature design of the trial product, a single group of target values recognized by experts in the clinical professional field is used for evaluation. In a given clinical setting, the use of non-randomized design is acceptable.

### **8.1.3 Measures to reduce and avoid bias**

In order to minimize and avoid the inherent bias of single group of target value design, the relatively objective and repeatable evaluation indexes are used in this study as the main evaluation indexes.

### **8.1.4 Investigational medical device**

Components and models of investigational medical device

Name of Component	Model
Stimulus unit	Qubic Stim – EP Heart Stimulator
Control unit	Qubic Stim – Control Unit
Patient cable	PK-128

### **8.1.5 Subject selection**

#### **8.1.5.1 Inclusion criteria**

The following inclusion criteria shall be met before patients are enrolled for cardiac electrical stimulation:

1. Age  $\geq 18$  years
2. Subjects who are willing to participate and sign the informed consent form, and are able to finish the follow-up at the study site.
3. Subjects with an indication of the intracardiac electrophysiological examination(fit one of the following):

- Paroxysmal supraventricular tachycardia: atrioventricular reentrant tachycardia or atrioventricular node reentrant tachycardia or atrioventricular tachycardia
- Ventricular arrhythmia: Premature ventricular contraction or ventricular tachycardia.
- Atrial fibrillation
- Atrial flutter

#### **8.1.5.2. Exclusion criteria**

1. Previous cases of unsuccessful radiofrequency ablation or recurrence
2. Pregnant and/or lactating women
3. Acute or severe systemic infection was present within 7 days prior to the intracardiac electrophysiological examination
4. Liver and kidney functions were obviously abnormal within 7 days prior to the intracardiac electrophysiological examination
5. Obvious bleeding tendency or blood system disease
6. Cancer and terminal disease
7. Combined with severe organic cardiovascular disease
8. Cerebral apoplexy and other cerebrovascular diseases within the past 3 months
9. Thromboembolic disease
10. Subjects who are participating in other interventional clinical trials

#### **8.1.5.3. Criteria and procedures for termination of trial / trial treatment**

When the study is completed or terminated, BIOTRONIK shall inform the investigators. Investigator shall return any investigational devices, equipment and relevant information they obtain at the request of BIOTRONIK. BIOTRONIK shall provide the final report to each study site. At the end of the study, BIOTRONIK will conduct a study closure visit, during which the BIOTRONIK shall verify the study records to ensure that the investigators can understand any applicable regulatory requirements, including those related to record keeping. After the date of termination or completion of the clinical trial, the investigators shall also keep the original documentation of the study for 10 years.

##### **(1) Suspension or early termination of study**

BIOTRONIK may terminate the study in advance or suspend the study due to the following circumstances:

BIOTRONIK monitors the safety after cardiac electrical stimulation by continuous evaluation of all adverse events related to cardiac stimulator. If serious adverse device events (SADE) affect the health and safety of the subjects, the study will be suspended until the cause of serious adverse device events is clarified. The study can only continue if the health and safety of the subjects are not affected. However, tachycardia events caused by any programmed stimulation will not cause the study to be suspended. Retraining is required if investigators fail to follow research protocols and regulations; if the investigator continues to fail to comply with the protocol and relevant regulations, the study will be suspended until the investigator is fully retrained and qualified.

In case of serious failure of investigational device due to cardiac electrical stimulation, all study sites shall immediately terminate the study.

## (2) Follow-up requirements of subjects

After suspension or early termination of the study, the investigator must notify all subjects (who may not have completed the study). The study site will ensure that attention is paid to the subjects.

### **8.1.5.4. Enrollment time**

106 cases are expected to be enrolled in this trial, and the enrollment is planned to be completed 3 months after the start of the trial. If the enrollment is not completed, the whole trial process will be postponed.

### **8.1.5.5. Expected overall duration of clinical trials and reasons for its determination**

In this study, data is collected, analyzed and reported to further determine the clinical effectiveness and safety of Qubic Stim cardiac stimulator in Chinese population, which provides a basis for the application of pre-market approval.

All subjects who meet the inclusion and exclusion criteria will receive the intracardiac electrophysiological examination after signing the informed consent, during which the heart will be given diagnostic electrical stimulation through the Qubic Stim cardiac stimulator. The subjects will also receive the clinical follow-up after cardiac electrical stimulation until they are discharged from the hospital.

In view of the three-month enrollment time, the whole study is expected to start in October 2020 and end in February 2021.

### **8.1.5.6 Predicted participation duration of each subject**

Each subject can be enrolled only after signing the informed consent form. After that, the subject will receive cardiac electrophysiology in accordance with clinical routine diagnosis and treatment procedures as scheduled by the investigators. When the subject completes the follow-up on the day of discharge, the study will be ended.

### **8.1.5.7 Subject number required in the clinical trial**

This study is a prospective, multicenter, single-arm, and interventional study with a sample size calculation for the main clinical observation indexes. In this trial, it is planned that 106 subjects will be enrolled.

## **8.1.6 Effectiveness evaluation method**

### **8.1.6.1 Description of effectiveness parameters**

Cardiac electrical stimulation is performed through the main function of the cardiac stimulator to achieve the corresponding expected clinical effect, which serve as the evaluation of clinical effectiveness.

### **8.1.6.2 Methods and time selection for evaluation, record and analysis of effectiveness parameters**

The device is used for diagnostic electrical stimulation of the heart, including induction and termination of tachyarrhythmia, refractory period measurement and electrical conduction measurement. The main functions of cardiac stimulator include:

1. Programmed extrastimulation (PES)

The expected clinical effect: the heart is effectively paced by PES at a set rate of stimulation.

2. High rate stimulation (Burst)

The expected clinical effect: when the tachycardia is induced or terminated by high-rate stimulation, the device can effectively pace the heart at a set rate of stimulation.

3. Measurement of sinus node recovery time (SNRT)

The expected clinical effect: the sinus node recovery time can be measured.

The success rate of the Qubic Stim cardiac stimulator to send diagnostic electrical stimulation to the heart. The success standard refers to that all the main functions of the cardiac stimulator meet the success standards. Cardiac electrical stimulation is performed

by the above main functions of the cardiac stimulator in this trial, and when the above three functions in particular subjects are up to the standards, it is judged as stimulation success. The main evaluation index corresponds to the proportion of the patients who reach the success standards.

The target value for the success of this trial is defined as not less than 90%.

### **8.1.7 Safety evaluation method**

#### **8.1.7.1 Description of safety parameters**

Serious adverse device events rate ( $P_{SADE}$ ) is used in this trial to evaluate clinical safety of Qubic Stim cardiac stimulator.

#### **8.1.7.2 Method and time selection for valuation, record and analysis of safety parameters**

All adverse events shall be recorded throughout the study. However, only the serious adverse events that are definitely, likely or possibly related to Qubic Stim cardiac stimulator will become the basis of SADE event rate.

SADE related to Qubic Stim cardiac stimulator is defined but not limited to: serious adverse device events caused by failure to start-up, current failure to output, leakage current and other reasons. These will be recorded as SADE related to Qubic Stim cardiac stimulator. But in cases where electrical stimulation is known to cause potentially life-threatening arrhythmias, many times inducing these arrhythmias is the purpose of an electrophysiological examination. Therefore, any tachycardia events caused by programmed electrical stimulation in this study will not be included in SADE.

The important parameter  $P_{SADE}$  is the rate of serious adverse events that may be related to Qubic Stim cardiac stimulator for each subject, which is equal to the number of SADE divided by the number of subjects.

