#### 9.1.2 Statistical analysis methods

1) Descriptive analysis: Counting data is described by frequency and constituent ratio; while measurement data is described by mean, standard deviation, median, the 25th and 75th quantiles, maximum, and minimum.

2) Baseline demographic analysis: Descriptive analysis will be the main method. For subgroups comparison that may be involved, the likelihood data  $\chi^2$  test will be used between counting data groups. When the theoretical frequency of more than 25% of the cells is less than 5, the Fisher exact probability method will be used. Grouped t-test is used for comparisons between groups with normally distributed measurement data; while Wilcoxon Rank Sum test used for comparisons between groups with non-normally distributed measurement data.

3) Efficacy analysis: All patients who use the investigational product will be included in the analysis. For the primary efficacy indexes, the asymptotic normal method and accurate probability method will be used to estimate the stimulation success rate and its 95% confidence interval, and the lower limit of the confidence interval are compared with the set target values to determine whether the test product meets the needs of clinical application. Meanwhile, the Tipping Point method will also be used to perform a sensitivity analysis on the potential impact of missing data. For the filled data, the asymptotic normal method and accurate probability method are also used to estimate the product success rate and 95% confidence interval, respectively. The statistical analysis method to be used for other efficacy indexes is the same as the baseline; for intra-group

comparisons that may be involved in specific indexes, paired t test is used for comparisons between groups with normally distributed measurement data; while Wilcoxon Rank Sum test used for comparisons between groups with non-normally distributed measurement data; and for intra-group comparison of qualitative indexes, the McNemar paired  $\chi^2$  test is used.

4) Safety evaluation: Adverse events are described by the number and incidence of adverse events; meanwhile, the specific manifestation, severity and relationship between all the adverse events are described in detail.

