5) For the main endpoint indexes, statistical analysis will be performed at a significance level of 0.025 on one side (corresponding to the one-sided confidence limit of the 95% confidence interval), and statistical analysis of other indexes will be performed at a significance level of 0.05 on both sides (unless otherwise stated). All the statistical analysis will be run on SAS®9.4 statistical software.

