## **9.4 Predicted drop-out rate**

In the sample size design process, the largest possible drop-out rate in the study period is expected to be 5%. The drop-out includes all cases that ultimately cannot be included in the main analysis, and usually refers to significant violations of the study protocol judged by the principal

investigator. The possible situations include (not limited to): patients do not meet the inclusion/exclusion criteria; patients do not use any study-related products; patients use third-party products other than the study; patients do not complete follow-up as required; follow-up time windows exceed the set time limit; there are concomitant treatments that affect efficacy. All of the above will be included in the total drop-out rate.

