## **9.9 Criteria for selection of subjects incorporated into the analysis and its reasons**

The statistical analysis will be performed on the basis of the following analysis populations, which will be clearly defined before the start of the statistical analysis. The analysis populations in this study include:

**Full Analysis Set (FAS):** An analysis set that is determined in accordance with the Intention To Treat principle, which will include all subjects who participates in the trial (recorded in the central registry) and do use the investigational product.

**Per Protocol Set (PPS):** refers to all subgroups of patients who have completed the trial without significant protocol deviation (referring to the study subject's violation of the inclusion/exclusion criteria, *etc.*).

**The analysis of the primary efficacy indexes will be performed on the basis of the FAS and the PPS; all baseline demographic data and secondary efficacy analysis will be performed on the basis of the FAS, and the safety evaluation will also be based on the FAS. (So SS is not defined separately).**

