### **14.4 Serious adverse events**

Serious adverse event (SAE) refers to adverse events occurring during the clinical trial which caused one of the following conditions:

- Death
- Serious aggravation of the health status, including:
  - Lethal diseases or damages;
  - Permanent defect of body structure or body function
  - Hospitalization treatment or prolonged hospital stays
  - Requiring medical or surgical intervention to prevent the permanent defect of body structure or body function;
- Fetal distress, fetal death, or congenital deformity, congenital defect, and etc.

The planned hospitalization before enrollment, surgeries required in the trial protocol, and events not causing serious aggravation of the health status are not regarded as SAEs. The medical or surgical interventions implemented to prevent the occurrence of life-threatening conditions are regarded as SAEs. For instance, the hospitalization due to pneumonia or hospitalization because of any surgical intervention is regarded as SAE. A new event occurring during hospitalization which prolonged the hospital stay (e.g., atrial fibrillation requiring cardioversion) is regarded as a new SAE, because two events had different diagnoses. The hospitalization before the aggravation of the health status (e.g., hospitalization due to the planned angiography) is not regarded as SAE.

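### P_SADE counts events rather than affected subjects and has no planned confidence interval, although the trial's stated aim includes proving safety

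*Combined protocol and SAP*

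**What the plan says.** Section 8.1.7.1 names one safety parameter, P_SADE, which "is used in this trial to evaluate clinical safety of Qubic Stim cardiac stimulator". Section 8.1.7.2 gives its formula: it is a rate "for each subject, which is equal to the number of SADE divided by the number of subjects".

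Section 14.4 says how serious events are counted. A further event with its own diagnosis that prolongs a hospital stay "is regarded as a new SAE, because two events had different diagnoses". Section 14.5 defines a SADE as a device event with the features of an SAE.

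For the safety analysis, section 9.1.2(4) says that "Adverse events are described by the number and incidence of adverse events", and adds a detailed description of manifestation, severity and relationship. Section 9.9 fixes the population: "the safety evaluation will also be based on the FAS".

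An interval is planned for the primary index only. Under section 9.1.2(3), "the asymptotic normal method and accurate probability method will be used to estimate the stimulation success rate and its 95% confidence interval". Section 9.1.2(5) adds that "statistical analysis of other indexes will be performed at a significance level of 0.05 on both sides", unless stated otherwise.

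The Protocol Summary and sections 4.1 and 8.1.1 give proof of effectiveness and safety as the aim, and section 4.2 speaks in the same terms. Section 9.5 judges the trial on stimulation success alone.

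**The concern.** There are two separate weaknesses.

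First, the description and the formula of P_SADE do not match. A per-subject rate suggests the share of subjects harmed, but the numerator is a count of events. If one subject has several SADEs, the figure overstates the share of subjects affected. Events within one subject are also not independent yes/no outcomes, and the ratio could in principle exceed 1, so the exact binomial method used elsewhere in the plan cannot be carried over to it.

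Second, the plan gives no measure of how precisely P_SADE is estimated. The sample of 106 was set for the success rate. For a rare device event, a trial of this size may well observe none. A bare 0%, in a report whose stated purpose is to prove safety, would not tell the reader what risk remains possible. What is at stake is the strength of the safety statement, not the trial's pass/fail decision.

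**Working it through.** **Inputs.** Planned enrolment is 106, with target 90%, expected rate 98%, one-sided level 0.025, power 90% and drop-out 5% (section 9.2.1). Safety is analysed in the FAS (section 9.9). The plan gives no expected value, target or precision for P_SADE, so the true risks used below (1%, 2%, 3%) and the clustered example are assumptions.

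**The plan's own figure.** The exact binomial method with 100 evaluable subjects requires at least 96 successes. This gives a one-sided type I error of 0.0237 and power of 0.949. Power is below 0.90 for n = 88 to 99 and at or above 0.90 for every n from 100 to 109, the largest checked. Then 100/0.95 = 105.3, rounded up to 106. The planned number is reproduced, from the success rate only.

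**What zero SADEs would show.** With 0 events in n subjects, the exact (Clopper-Pearson) two-sided 95% upper limit is 1 − 0.025^(1/n).

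- n = 106: 1 − 0.025^(1/106) = 0.0342, or 3.42%.
- n = 101: 1 − 0.025^(1/101) = 0.0359, or 3.59%.

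The second case comes from section 9.4, where "the largest possible drop-out rate in the study period is expected to be 5" per cent: 106 × 0.95 = 100.7, taken as 101. It assumes that every drop-out never used the device. Section 9.4 also counts as drop-outs subjects who used it but, for example, missed follow-up; they stay in the FAS. So 101 is a cautious lower case.

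**How often zero would be seen.** The probability is (1 − p)^n for a true per-subject risk p.

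| True risk p | n = 106 | n = 101 |
|---|---|---|
| 1% | 34.5% | 36.2% |
| 2% | 11.7% | 13.0% |
| 3% | 4.0% | 4.6% |

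**Effect of the numerator.** Assume three SADEs, all in one subject, and 106 subjects.

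- Formula as written: 3/106 = 2.83%.
- Share of subjects affected: 1/106 = 0.94%. The exact limits are the 0.025 quantile of Beta(1, 106) and the 0.975 quantile of Beta(2, 105), that is 0.02% to 5.14%.
- Binomial interval put on 3/106: the 0.025 quantile of Beta(3, 104) and the 0.975 quantile of Beta(4, 103), that is 0.59% to 8.05%. This is not valid here, because the three events come from one subject.

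If no subject has more than one SADE, the two numerators are equal. With zero SADEs both formulas give 0%, so the numerator has no bearing on the zero-event case.

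**The case against.** The other side has a fair case. Descriptive safety reporting is usual in a study sized for its primary endpoint. Section 9.5 tests no safety claim. P_SADE is not the only safety evidence: all adverse events and device deficiencies are recorded, events are described in detail, and sections 5 and 8.1.2 rely on an earlier clinical evaluation. Several SADEs in one subject are improbable between a single examination and discharge, and section 14.4 concerns SAEs in general. Incidence in section 9.1.2(4) can be read as per subject. Any reader can work out the interval from the count and the denominator.

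Much of this stands, and it keeps the point small. It does not remove it. An interval is itself description and needs no test, margin or larger sample. Reading incidence as per subject conflicts with the explicit formula in section 8.1.7.2.

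Two parts of the plan might seem to supply the interval already. Section 9.1.2(5) sets a two-sided level for other indexes but names no interval or method for P_SADE, and the item specific to safety is descriptive. Section 9.7 leaves to the statistical analysis plan only the handling of missing primary efficacy data, and section 9.8 says that main methods will in principle not change. No separate analysis plan is in the document reviewed.

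A reader might also infer that the SADE definition contradicts itself, because the Protocol Summary, section 8.1.7.2 and section 14.5 word it differently and only section 8.1.7.2 states the tachycardia exclusion. The text does not support that. Section 14.5 reads naturally together with 8.1.7.2. The suspension rule in 8.1.5.3 points the same way, the footnote on programmed extra stimulation gives the term a broad meaning, and 8.1.7.2 expressly lists device failures as causes of SADEs.

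**Conclusion.** The point holds as a cheap improvement. P_SADE as written is events over subjects. It departs from the share of subjects affected only if a subject has more than one SADE; the 2.8% against 0.9% contrast rests on an assumed example. Independently of that, no interval is planned. Zero SADEs among 106 would leave a per-subject risk of up to 3.4% open, or 3.6% if only 101 subjects used the device.

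Three stronger readings are not supported. Zero SADEs is not a likely result at a true risk of 1% to 2%: at least one would be seen in about 65% and 88% of such trials (1 − 0.345 and 1 − 0.117). The choice of numerator does not create the zero-event problem. And nothing in the plan says that 0% would be taken as proof; that is an inference from an aim of proving safety with no safety criterion beside it. The primary endpoint, the sample size and the rule in section 9.5 are unaffected. If a separate analysis plan already specifies an interval for the subject-level proportion, only the definition in section 8.1.7.2 needs correcting.

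**What to change.** 1. In section 8.1.7.2, define P_SADE as the number of FAS subjects with at least one SADE divided by the number of FAS subjects. Report the total number of SADEs separately.
2. In section 9.1.2(4), add an exact (Clopper-Pearson) two-sided 95% confidence interval for P_SADE.
3. In the clinical trial report, state the safety conclusion with that interval, for example 0/106 with an upper limit of 3.4%.

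The cost is wording in two sections and one extra line of output. All adverse events are already recorded, the FAS is already the safety population, and the exact method is already in the plan, so no new data are needed. The purpose statements can stay as they are. The one drawback for the sponsor is that the safety statement may look slightly less favourable than a bare percentage.
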